7.2.1 Pre-Screen Medical Chart Review – Initial determination of eligibility and recruitment

Patients who have an upcoming usual care appointment with a study hepatologist will be identified and pre-screened for eligibility based on the most updated information in their medical charts, prior to their visit. The medical records will be reviewed by the clinical research staff to determine initial eligibility as specified in the inclusion and exclusion criteria. Medical charts will be reviewed for age, cirrhosis diagnosis, prior liver transplant, prior statin use, prohibited concomitant medications, previous malignancies, medical contraindications, laboratory results, and evidence of HCC from last abdominal image (ultrasound, computed tomography (CT), or magnetic resonance imaging (MRI)) occurring within the past 18 months. If a patient's lab results in the medical record do not meet the eligibility criteria, the patient may still be considered potentially eligible because blood tests will be done at the Screen 1 visit. The research staff will notify the study hepatologist that a patient is potentially eligible for the trial based on the pre-screen evaluation. The hepatologist will review the eligibility information and notify research staff whether the patient may be considered for participation. An information packet that introduces the study may be mailed to potentially eligible patients who may be considered for participation. The packet will include the study consent form (ICF), HIPAA authorization, and IRB-approved recruitment materials (e.g., introductory letter, leaflet; each participating site will choose what materials to include). One of the study hepatologists or clinical research staff will call potentially eligible patients before their scheduled appointment to introduce the study and answer questions. Patients will be encouraged to review the consent documents with family, friends, and/or other physicians. The patient will be told that the decision to join or not join the study will not affect the medical treatment that s/he receives, and that s/he can

withdraw from the study at any time. Patients who wish to participate will be consented into the trial at their next standard of care visit with a study hepatologist.

For potentially eligible patients who may not be mailed a recruitment packet in advance of the regular clinic visit (e.g., new patients or patients added to the schedule late), a study hepatologist will introduce the study to the patient during the standard of care clinic visit. The patient may be given a study information packet to take home for review. Clinical research staff will be present at the clinic during this visit and will be available to review the materials in the information packet with the patient and answer questions about the study. Clinical research staff will follow-up with a phone call to the patient a few days later to evaluate interest in study participation and answer additional questions. Interested patients will be scheduled to sign informed consent documents with the study hepatologist or a member of the clinical research team. Patients who have had all their questions about the study answered on the day they first learn about the study, and who wish to participate, may be consented the same day they are first informed of the research.

7.2.2 Screen 1 – Consent, Final determination of eligibility, Registration, and Randomization

The study hepatologist will review the study details and answer any questions regarding the proposed trial after all clinical options have been presented to the patient. After the patient's questions have been answered, the study hepatologist will obtain signatures on the consent documents from patients who are eligible based on the pre-screen chart review and wish to volunteer for the study. Patients for whom Spanish is their preferred language will be consented using a version of ICF translated into Spanish, administered by an interpreter. The patient will carefully review and sign the study consent form and HIPAA authorization. Copies of each form will be given to the patient and placed in the medical record. Written consent will be obtained before any research related procedures are initiated. Participants who sign consent will be provided a copy of Appendix D (Food and Medications to Avoid During Your Participation in the Study).

After consent has been obtained, a final assessment of eligibility will be conducted. Consented patients will undergo additional screening and testing to confirm eligibility and safety of statin initiation.

- 1. The study hepatologist will thoroughly review the patient's medical history, concomitant medications, and laboratory test results.
- 2. All inclusion and exclusion criteria will be evaluated for the patient.
- 3. Symptom assessment and ECOG performance status
- 4. Physical assessment including vital signs, measurement of weight, and assessment of liver disease sequelae (varices, ascites, and encephalopathy)
- 5. A blood specimen (approximately 15 mL) will be collected from patients for blood tests to confirm eligibility. If a patient's lab results are current (within the past 30 days) in the medical record and within eligibility range, their blood will not be drawn at the Screen 1 visit. Otherwise, the patient's blood will be drawn to confirm eligibility. A Complete Blood Count and Automated Differential (CBDF) (for leukocytes, neutrophils, platelets, and hemoglobin), a Comprehensive Metabolic Panel (CMPL) (for liver enzymes (AST/ALT) and for total bilirubin, creatinine, and sodium (required for calculation of the MELD score)), and Prothrombin Time (PT/INR) (required for calculation of MELD) will be done to confirm that blood levels are within the eligibility requirements (acceptable organ function, AST/ALT ≤5x upper limits of normal, and MELD ≤ 20). See Appendix E for Clinical Laboratory Minimum Test Requirements.
- 6. Women who are able to become pregnant will be required to have a pregnancy test because statins are known to be teratogenic. Women ≥ 50 years of age who have not had a menstrual

period in the past year; and women who have had a hysterectomy, both ovaries removed, or a tubal ligation; will not be required to have a pregnancy test.

Patients with a MELD score >20, AST/ALT >5x ULN, or other lab results that do not meet the eligibility criteria; and women who are pregnant will be excluded from the study. Following eligibility screening, and prior to Study Visit 1, consented patients who qualify for the study after the eligibility evaluations will be registered and enrolled in the study and randomized to the intervention (simvastatin or placebo). The Screen 1 MELD calculation will be used as the baseline MELD score, and Screen 1 lab values for AST, ALT, and platelets (PLT) will be used to calculate the baseline FIB-4 score.

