Medical history, medications, and laboratory test results review. Medical history, concomitant medications, and laboratory test results will be reviewed at Study Visits 1, 2, 3, and 4 by one of the study hepatologists or the clinical research staff.

Vital signs and symptom assessment. Participants will have a vital signs and symptom assessment at Screen 1 and Study Visits 1, 2, 3, and 4. Each assessment will include an interval symptom history; ECOG performance status; vital signs, including blood pressure, heart rate, and temperature; and measurement of weight. Height will be measured at Study Visit 1. A physical assessment, including assessment of liver disease sequelae (varices, ascites, and encephalopathy) will be done at Screen 1 and Study Visit 4.

Blood specimen. A blood specimen (approximately 15 mL) will be collected from patients at the Screen 1 eligibility visit for blood tests to confirm eligibility. If a patient's lab results are current (within the past 30 days) in the medical record and within eligibility range, their blood will not be drawn at the Screen 1 visit. Otherwise, the patient's blood will be drawn to confirm eligibility. A Complete Blood Count and Automated Differential (CBDF), a Comprehensive Metabolic Panel (CMPL), and Prothrombin Time (PT/INR) will be done to confirm that blood levels are within the eligibility requirements (acceptable organ function, $AST/ALT \leq 5x$ upper limits of normal, and MELD ≤ 20).

A blood specimen (approximately 10-15 mL) will be collected from each participant at Study Visits 1, 2, 3, and 4 for laboratory blood tests to monitor for potential adverse effects of the intervention. A Lipid Panel and hemoglobin A1C will be done at Study Visits 1, 3, and 4. A Complete Blood Count and Automated Differential (CBDF) and Comprehensive Metabolic Panel (CMPL) will be done at Study Visits 2, 3, and 4. Creatine Phosphokinase (CPK) will be measured at Study Visit 1. Prothrombin Time (PT/INR) will be done at Study Visit 4 to calculate the MELD score. Clinical lab results from Screen 1 and Study Visit 4 will be used to calculate the MELD and FIB-4 scores.

An additional blood specimen (20 mL) will be collected from each participant at Study Visits 1 and 4 for research purposes. Ten mL of blood will be drawn for measurement of protocol-specific biomarkers (AFP, AFP-L3%, IL-6, and bile acids) and 10 mL of blood will be drawn for DNA extraction and use in future studies.

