7.2.3 Study Visit 1 – Baseline Testing and Initiation of the intervention

Study Visit 1 (Baseline measurements) will occur 0-30 days after the Screen 1 eligibility visit. The following procedures will be performed during this visit:

- 1) Review of medical history, medications, and laboratory test results
- 2) Symptom assessment and ECOG performance status
- 3) Vital signs assessment, including blood pressure, heart rate, and temperature; and measurement of height and weight
- 4) Blood collection for clinical labs (approximately 10 mL). Laboratory blood tests will be done for a Lipid Panel, hemoglobin A1C, and Creatine Phosphokinase (CPK) to establish baseline levels prior to initiating the study agent. CBDF and CMPL lab results from the Screen 1 eligibility visit will be used to establish patient-specific references prior to initiation of therapy. If blood tests were not done at the Screen 1 visit for a CBDF and CMPL; and lab results within 30 days prior to this visit for these tests are not available in the medical record, a CBDF and CMPL will be done at this visit. See Appendix E for Clinical Laboratory Minimum Test Requirements.
- 5) Blood collection for research (20 mL). Ten mL of blood will be collected for measurement of protocol-specific biomarkers (AFP, AFP-L3%, IL-6, and bile acids) and 10 mL of blood will be drawn for DNA extraction and use in future studies.
- 6) Liver elastography (FibroScan). A FibroScan examination will be conducted. Participants will be instructed to refrain from eating for 3 hours before the FibroScan examination. The FibroScan will be used as a non-invasive measurement of liver stiffness.
- Interviewer-administered baseline questionnaire to obtain demographic information (detailed race and ethnicity, education); medical and medications history; alcoholic beverage consumption; tobacco smoking; and anthropometry (Appendix F)
- 8) Food frequency questionnaire (FFQ). The VioScreen[®] graphical dietary assessment will be selfadministered to capture usual diet over the last 30 days.
- 9) Review of study requirements
- 10) Dispense the study agent (one bottle of 120 capsules) and review instructions for how to take it
- 11) Dispense and review the study diary

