7.4 Evaluation at Completion of the Study Intervention

7.4.1 Study Visit 4

The final study visit will occur 6 months (\pm 30 days) after initiation of the intervention. Study Visit 4 is concurrent with a standard of care visit. The following procedures will be performed during this visit:

- 1) Review of medical history, medications, and laboratory test results
- 2) Symptom assessment and ECOG performance status
- 3) Physical assessment including vital signs, measurement of weight, and assessment of liver disease sequelae (varices, ascites, and encephalopathy)
- 4) Blood collection for clinical labs (approximately 15 mL). Laboratory blood tests will be done for a CBDF, CMPL, Lipid Panel, and hemoglobin A1C to monitor for potential adverse effects of the intervention; and for measurement of Prothrombin Time (PT/INR) to calculate the MELD score. Clinical lab results (AST, ALT, and platelets (PLT)) will also be used to calculate the FIB-4 score. If lab results within 30 days prior to this visit for any of these tests are available in the medical record, the blood test(s) will not be repeated. See Appendix E for Clinical Laboratory Minimum Test Requirements.
- 5) Blood collection for research (20 mL). Ten mL of blood will be collected for measurement of protocol-specific biomarkers (AFP, AFP-L3%, IL-6, and bile acids) and 10 mL of blood will be drawn for DNA extraction and use in future studies.
- 6) Liver elastography (FibroScan). A FibroScan examination will be conducted. Participants will be instructed to refrain from eating for 3 hours before the FibroScan examination. The FibroScan will be used as a non-invasive measurement of liver stiffness.

- 7) Abdominal imaging. An abdominal image (CT, MRI, or ultrasound) will be taken for standard of care HCC surveillance. The abdominal imaging may be done up to the end of follow-up for the study (3 months after completion of Study Visit 4 [Visit 4 ± 3 months]).
- 8) Collect study agent and diary
- 9) Assess compliance (pill count)
- 10) Review study diary
- 11) Assess adverse events

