8. CRITERIA FOR EVALUATION AND ENDPOINT DEFINITION

The overall objective of this trial is to examine the effects of simvastatin use versus placebo at 6 months from baseline (Study Visit 1) on liver function in high-risk patients with liver cirrhosis who have a current Model for End-Stage Liver Disease (MELD) ≤ 20 and no evidence of hepatocellular carcinoma (HCC). Participants will be on the study drug from Study Visit 1 until the last study visit (Study Visit 4 at 6 months). Primary and secondary endpoints are measured in blood samples.

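### Baseline MELD and FIB-4 may come from labs up to 60 days before Visit 1, and the 6-month scores from labs at about month 4, although newer results exist or could be obtained cheaply

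*Combined protocol and SAP*

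**What the plan says.** Section 8 sets the trial's overall objective "at 6 months from baseline (Study Visit 1) on liver function in high-risk patients". For two secondary endpoints the baseline is taken elsewhere. Section 7.2.2 takes baseline MELD from the calculation made at Screen 1. For the other score it states that "Screen 1 lab values for AST, ALT, and platelets (PLT) will be used to calculate the baseline FIB-4 score". Section 3 (Blood specimen) agrees: "Clinical lab results from Screen 1 and Study Visit 4 will be used to calculate the MELD and FIB-4 scores".

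The Screen 1 values need not come from blood drawn at Screen 1. Under Section 7.2.2 no draw is made when "If a patient's lab results are current (within the past 30 days) in the medical record and within eligibility range". Section 7.2.3 then adds that "Study Visit 1 (Baseline measurements) will occur 0-30 days after the Screen 1 eligibility visit".

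Section 7.2.3 also calls for a blood count (CBDF) and metabolic panel (CMPL) at Visit 1 if neither was drawn at Screen 1 and the chart has nothing from the 30 days before Visit 1. PT/INR is not part of that rule; Section 7.1 and Appendix E schedule it only at Screen 1 and Visit 4.

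Section 7.4.1 places Visit 4 at 6 months ± 30 days and waives repeat testing by this rule: "If lab results within 30 days prior to this visit for any of these tests are available in the medical record". The waiver covers the CBDF, CMPL and PT/INR, from which both scores are calculated.

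**The concern.** MELD and FIB-4 are reported as change over 6 months from baseline, beside AFP-L3%, AFP, IL-6, bile acids and liver stiffness, which are all measured at Visits 1 and 4 themselves. The two lab-based scores can cover a different and more variable period.

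Three things are at stake:

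- **Precision.** Section 13.5 compares arms by ANCOVA with the baseline value as a predictor. Residual variance is proportional to 1 − ρ², where ρ is the correlation between baseline and outcome. An older baseline will usually correlate less well with the outcome, so the treatment effect is estimated less precisely.
- **Dilution.** If an effect is still building between months 4 and 6, a month-4 lab misses part of it. Section 3 justifies 6 months of treatment partly because an earlier statin study saw AFP fall at 6 months but not at 3. That finding concerns AFP, not MELD or FIB-4, but it shows that the planners thought timing mattered.
- **Consistency.** The plan treats a blood count or panel more than 30 days old as too old to serve as a reference before therapy starts, yet it keeps the same result as the efficacy baseline.

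**Working it through.** **Inputs**

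- Age of chart labs accepted at Screen 1: up to 30 days (Section 7.2.2).
- Screen 1 to Visit 1: 0 to 30 days (Section 7.2.3).
- Visit 4 window: 6 months ± 30 days (Section 7.4.1).
- Age of chart labs accepted at Visit 4: up to 30 days (Section 7.4.1).
- Six months taken as 180 days (30-day months) or about 183 days (30.44-day months).

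**1. The plan's own figure.** Section 7.6 describes the Screen 1 CBDF and CMPL blood as at most 30 days old at Visit 1. For blood drawn at Screen 1 this is right: 0 + 30 = 30 days.

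**2. The chart route.** When chart labs replace the draw, the maximum age at Visit 1 is 30 + 30 = 60 days. This exceeds the 30 days in Section 7.6.

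**3. Is a newer pre-dose result available?** Suppose the baseline CBDF/CMPL is 31 to 60 days old at Visit 1. Then it was not drawn at Screen 1, because a drawn sample would be at most 30 days old. The first condition in Section 7.2.3 is therefore met. Either the chart holds a result from the 30 days before Visit 1, or a new CBDF and CMPL are drawn at Visit 1. In both cases newer AST, ALT, platelets, bilirubin, creatinine and sodium exist before the first dose. No section says that they replace the Screen 1 values. INR is the exception, since nothing triggers a newer one.

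**4. Earliest and latest 6-month lab.**

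- Earliest: 180 − 30 − 30 = day 120 (183 − 60 = day 123).
- Latest: 180 + 30 = day 210 (183 + 30 = day 213).

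**5. Lab-to-lab interval, 30-day months.**

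- Shortest: 120 − 0 = 120 days (4 months).
- Longest: 210 + 60 = 270 days (9 months).
- Spread: 270 − 120 = 150 days. Of this, 60 days come from the Visit 4 window, which applies to every endpoint. Another 30 come from the Screen 1 to Visit 1 gap, 30 from chart labs at Screen 1 and 30 from chart labs at Visit 4.

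**6. Which components can differ in date at Visit 4.** The waiver applies test by test. Bilirubin, creatinine and sodium belong to one panel, the CMPL. In MELD, INR can therefore come from a different day than the other three. In FIB-4, platelets (CBDF) can come from a different day than AST and ALT (CMPL).

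**7. After the change proposed below.**

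- CBDF/CMPL baseline age: 0 to 30 days, because a Screen 1 draw, a recent chart result or a Visit 1 draw always meets that limit.
- Follow-up lab at an in-person Visit 4: day 150 to 210.
- FIB-4 interval: 150 to 210 + 30 = 240 days, against 120 to 270 now.
- If all components were drawn at Visits 1 and 4 themselves: 150 to 210 days.

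**The case against.** The best defence is that this is a stated choice. Sections 3 and 7.2.2 both name Screen 1 and Visit 4 as the sources for these scores. Section 8 mentions Visit 1 in a general objective, and Section 13.1 attaches it to AFP-L3%, so the endpoint-specific rule governs. Screen 1 labs also precede randomisation. This shows that the baseline rule does not breach the plan. It does not explain why a value up to 60 days old is kept when a newer one is on file. A Visit 1 value is still pre-dose, in a double-blind trial, and Visit 1 is already the baseline for the other endpoints.

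It can also be said that the Section 7.2.3 redraw means only INR necessarily lacks a newer value at 60 days, and that the phrase about Screen 1 lab values is ambiguous when no Screen 1 draw took place. Both are fair, and both argue for one clarifying sentence.

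Several stronger readings are tempting but not supported:

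- **That the comparison between arms is biased.** A reader might infer this because in-range chart labs are accepted while out-of-range ones are redrawn, which invites regression to the mean. That affects within-arm change. The same rule applies to both arms, and Section 13.5 adjusts for baseline.
- **That an old baseline captures the period before an effect has accrued.** Every baseline value is pre-dose in any case. Only the Visit 4 waiver can catch an effect too early.
- **That a fixed share of the effect is lost.** Linear build-up would give 123/183 = 67% at the earliest permitted lab. No section supports linear build-up for MELD or FIB-4, and the figure needs the earliest visit and the oldest chart lab together.
- **That the whole 120 to 270 day range is due to lab substitution.** Step 5 shows that 60 of the 150 days are the ordinary Visit 4 window.
- **That bilirubin and creatinine would carry different dates.** They share a panel.

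**Conclusion.** The point stands as a precision and definition problem in two of the six secondary endpoints. Baseline MELD and FIB-4 may rest on labs up to 60 days before Visit 1, twice the age that Section 7.6 describes, even though a newer pre-dose CBDF/CMPL exists whenever that limit is passed. The 6-month scores may rest on labs from about day 120–123, and INR or platelets may carry a different date from the rest of the score.

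These are the limits that the plan's windows allow, not typical values. The documents do not say how many participants would have chart labs used, and they give no power or variance for MELD or FIB-4, so the loss cannot be quantified. Dilution occurs only if an effect is still growing after month 4. The rules are the same in both arms, so the expected cost is noise and possible attenuation, not a directional error. AFP-L3%, the primary endpoint, is measured on research blood from Visits 1 and 4 and is not affected. The change is worth making because part of it costs nothing and the rest is cheap.

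**What to change.** 1. **Sections 3 and 7.2.2:** define baseline FIB-4, and the CMPL components of MELD, as the last values before the first dose. Keep Screen 1 labs for eligibility. This uses results that the plan already produces, so it adds no test.
2. **Sections 7.1, 7.2.3, 7.6 and 10.2:** reconcile them. The schedule ticks CBDF and CMPL at Visit 1 without condition, while the three text sections make them conditional. Correct the 30-day statement in Section 7.6 so that it covers the chart route.
3. **Section 7.4.1:** where Visit 4 is in person, do not apply the 30-day chart waiver to CBDF, CMPL and PT/INR, so that both scores come from the same visit.
4. **Lab dates:** record the actual date of every component at both ends, so that the intervals can be reported and examined.
5. **Optional:** add PT/INR to the Visit 1 draw. Without it, baseline MELD would combine a Screen 1 INR with later CMPL values whenever the panel is newer.

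The cost is a few routine local tests. Clinical and research blood is already drawn at Visit 1 and research blood at Visit 4, so most could use a planned draw. A reader should not assume that no one needs an extra needle-stick. Section 10.1 allows clinical tests at an outside laboratory required by the participant's insurer, which may mean a separate draw, and Sections 5.7 and 7.3.3 foresee remote visits. For remote visits the chart waiver may have to stay, with the lab date recorded.
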